3.6.3.3 Specifications

SBRT treatments are to be delineated using CT-based planning with custom thermoplastic mask for immobilization. SBRT is to be delivered using linear accelerators commissioned to deliver SBRT such as CyberknifeTM M6 (Accuracy, Inc., Sunnyvale, CA) TrilogyTM or TrueBeamTM STx (Varian Medical Systems Inc., Palo Alto, CA), with daily image guidance to

set-up verification and assessment of intra- and inter-fraction motion.

3.6.4 Follow-up/Long-term follow-up/Extended long-term follow-up procedures

Follow-up evaluations will be completed in patients in both arms (SBRT and wait-and see). They will be carefully followed every 3-6 months for 24 months or until death. Evaluations will consist of the following:

- Interim medical history and physical examination
- Careful documentation of Toxicity According to National Cancer Institute Common Toxicity Criteria Events Scale version 4.0
- Follow-up Patient-Reported Quality of Life Assessment (PR-QoL)
- FDG PET-CT at 8-12 weeks post-treatment then every 12 weeks

TABLE 1: Treatment Schema

		Clinical Visit			
Assessment		Pre-Study	During 8-12 weeks	Q 12-24 weeks	SBRT Post for 2-years
	History + Physical	X	X	X	X
	Imaging	X	X	X	
	QoL Assessment	X	X	X	

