3.5 Timeline of study procedures

Once eligible by screening and enrolled in study, patients will be randomized into one of two arms. One arm will receive SBRT treatment for 1 – 2 weeks. The second arm will receive no SBRT and will continue with standard of care treatment. Patients will be followed for 8-12 weeks after treatment and every 3-6 months for up to 24 additional months. Extended long-term follow-up will occur as clinically indicated until death.

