3.6.3.2 Randomized Arm

Patients randomized to the adjuvant SBRT arm will receive 40-50Gy in 5 fractions on non-consecutive days in 1-2 weeks on an outpatient basis. SBRT should be completed at a minimum of 4-weeks following salvage surgery, with a maximum of 12-weeks. CTV (clinical target volume) will represent the tumor bed/high-risk region as defined by head and neck surgeon and radiation oncologist. A maximum of 5mm expansion from CTV to PTV (planning target volume) shall be applied

Treatment Volumes $< 25\text{cc}$ will receive 40Gy (5 fractions of 8 Gy per fraction)
 Treatment Volumes $\geq 25\text{cc}$ will receive 44-50Gy over 5 fractions (5 fractions of 8.8Gy per fraction). Ideally, all tumors volumes $\geq 25\text{cc}$ will receive 50Gy over 5 fractions; however, at the discretion of the treating radiation oncologist based on tumor volume, prior radiation dose and proximity to critical organs, the dose can be reduced to 44Gy over 5 fractions as outlined in prior SBRT protocols.

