5.0 TREATMENT EVALUATION, ADMINISTRATION, AND MODIFICATION

5.1 Primary outcome variables to be evaluated

- (1) Primary endpoint - local progression-free survival (LPFS), defined as the time from the date of randomization to the date of local progression or the date of death from any cause. Subjects who are alive and have not progressed will be censored at their last follow-up date.
- (2) Regional PFS, distant PFS, PFS (local + regional + distant): The definition of these endpoints is similar to LPFS.
- (3) Overall Survival: time from the date of randomization to the date of death due to any cause.
- (4) Acute and late toxicities of adjuvant SBRT. Acute toxicity is defined as toxicity occurring within 3 months of completion of SBRT. Late toxicity is defined as toxicity occurring later than 3 months after SBRT treatment.

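### Section 3.6.4 gives conflicting scan intervals for the imaging that largely dates local progression, so compliant scan spacing can differ about twofold between patients and, if it drifts, between arms

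*Combined protocol and SAP*

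**What the plan says.** Section 3.6.4 opens by applying one schedule to everyone: "Follow-up evaluations will be completed in patients in both arms (SBRT and wait-and see". Its next sentence sets the frequency, "They will be carefully followed every 3-6 months for 24 months or until death", and introduces a list of what those evaluations contain. The last item in that list is "FDG PET-CT at 8-12 weeks post-treatment then every 12 weeks".

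Table 1, in the same section, has a column for visits every 12 to 24 weeks, and imaging is one of its rows. The table's headers are damaged in the text available, so I do not rely on which mark belongs to which column. Section 3.5 repeats the wider range for follow-up in general, "every 3-6 months for up to 24 additional months", without mentioning imaging.

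The primary endpoint in section 5.1 is LPFS, "defined as the time from the date of randomization to the date of local progression or the date of death from any cause". Section 3.6.5 names CT, PET/CT or MRI as the best available ways to measure disease status. For the control arm, section 3.5 says: "The second arm will receive no SBRT and will continue with standard of care treatment". No passage describes masking, a window around each scan, or scan weeks counted from a date that both arms share.

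**The concern.** A progression found on a scan is dated at that scan, so wider spacing means later recorded dates and a higher apparent LPFS. A visit cycle that may run to six months cannot deliver a 12-weekly scan, so the lead sentence and the bullet of section 3.6.4 conflict without any help from Table 1. A clinician could follow either and believe the protocol was being met.

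Two things are at stake. If spacing drifts equally in both arms, the comparison survives but the absolute one-year LPFS depends on how often patients were scanned. If spacing drifts differently by arm, the log-rank test compares intensity of looking as well as treatment. Nobody is described as masked and controls simply continue usual care, so the second kind of drift is possible. Once scans have been missed it cannot be undone in the analysis.

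**Working it through.** **1. The intervals in weeks.** Three to six months is 52/4 = 13 to 52/2 = 26 weeks (section 3.5 and the 3.6.4 lead sentence). Table 1 gives 12 to 24 weeks and the 3.6.4 bullet 12 weeks. The longest compliant spacing is thus 24/12 = 2.0 to 26/12 = 2.2 times the shortest. I compare 12 with 24 weeks below.

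**2. The plan's own figure (section 6.2).** Inputs: one-year LPFS 20% and 52%, one-sided alpha 0.10, power 90%, two years' accrual plus one year, 5% loss.
- Hazards per year: -ln 0.20 = 1.609 and -ln 0.52 = 0.654. HR = 0.654/1.609 = 0.406.
- Events (Schoenfeld): 4 × (1.2816 + 1.2816)² / (ln 0.406)² = 26.28/0.811 = 32.4, so 33.
- With uniform accrual and loss read as 5% a year, the mean event probability is 0.799. 33/0.799 = 41.3 patients, or 21 per arm.

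The stated 21 per arm reproduces and is not in question.

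**3. Effect on one-year LPFS.** Let S(w) be true LPFS at week w, L the last scan at or before week 52, and p the share of first events that only a scan would find. Then

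observed one-year LPFS = S(52) + p × [S(L) - S(52)].

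Assumptions not in the documents: exponential times; 20% of first events are deaths; 0-50% of progressions are found clinically between scans. So p = 0.8 × 1 = 0.8 down to 0.8 × 0.5 = 0.4. The first scan is assumed at week 14. The documents do not fix that week: the bullet counts from the end of treatment, and section 3.6.3.2 ties SBRT to surgery ("SBRT should be completed at a minimum of 4-weeks following salvage surgery, with a maximum of 12-weeks"), not to randomization.
- Scans every 12 weeks fall at 14, 26, 38, 50, so L = 50. Every 24 weeks they fall at 14, 38, so L = 38.
- Control: S(50) = 0.213, S(38) = 0.308. Observed 20.5-21.0% at 12 weeks and 24.3-28.7% at 24.
- SBRT: S(50) = 0.533, S(38) = 0.620. Observed 52.5-53.1% at 12 weeks and 56.0-60.0% at 24.
- Shift from 12 to 24 weeks: control p × 0.096 = 3.8 to 7.7 points; SBRT p × 0.087 = 3.5 to 6.9 points. In round terms, 4-8 points per arm.
- First scan at week 18: 18, 30, 42 against 18, 42. L = 42 on both, so the shift is zero.

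**4. Effect on the log-rank test.** Simulation with 21 per arm under the same assumptions, first scan at week 14, censoring uniform over 1-3 years, 3,000-5,000 trials per setting. Type I error uses the control hazard in both arms.

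| Scan spacing | One-sided type I error (nominal 0.10) | Power (nominal 0.90) |
|---|---|---|
| Same in both arms | about 0.10 | about 0.90 |
| Half of each arm at 24 weeks | 0.10-0.11 | 0.89-0.90 |
| 25% of controls, 50% of SBRT at 24 weeks | 0.11-0.13 | – |
| All controls 12, all SBRT 24 | 0.15-0.23 | – |
| All controls 24, all SBRT 12 | 0.04-0.08 | 0.81-0.88 |

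**5. Sensitivity, all controls at 12 weeks and all SBRT at 24.** With the first scan at week 18, type I error is still about 0.14-0.21, because the log-rank test uses the whole curve. With both arms at 52% one-year LPFS, it is 0.12-0.16. In the harshest setting tried (first scan at week 10, every event dated by a scan), it is 0.29.

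**The case against.** The strongest reply is that the passages can be read together. The bullet is the only prose that sets a scan interval, section 3.5 does not mention imaging, and 12 weeks lies inside Table 1's range and is close to three months. Scanning every 12 weeks would satisfy every passage, near enough. That is true, but it shows only that one compliant schedule exists. The lead sentence of 3.6.4 governs a list that contains the scan, so a six-month scan can also be defended as compliant.

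A reader might infer that the plan schedules the two arms differently. It does not: section 3.6.4 applies one list to both arms. Nor can the conflict be blamed on differing practice between sites, since section 3.4 places all study visits in one department.

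A reader might also infer that the 10% error rate is lost. The documents do not support that. The large departures need a whole arm on each interval, which no passage describes. Loose wording alone would more naturally produce similar drift in both arms, and then the test holds.

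Finally, a dedicated scan at month 12 may seem necessary. It is not needed for the primary comparison, which is a log-rank test over all follow-up (sections 6.2 and 6.4). It also does not generally fit a 12-week grid: with a first scan at week 10, scans fall at weeks 46 and 58.

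**Conclusion.** The inconsistency is real, is in the current text, and concerns the measurement that largely dates the primary endpoint. Its certain consequence is that the plan does not fix how often progression is looked for, to within a factor of about two. Its consequence for the treatment comparison is conditional: near nothing under equal drift, slight under moderate imbalance, and material only if spacing differs systematically by arm. The absolute one-year LPFS is exposed even under equal drift, by up to about 8 points with a first scan at week 14, though by nothing at week 18.

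The existence of the conflict rests on the prose of section 3.6.4 alone. The sizes rest on assumed first-scan timing, the share of events found only on scans, and exponential times, none of which the documents give. With 42 patients and no masking described, it is worth closing by wording now.

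**What to change.** Reconcile the lead sentence of 3.6.4, the PET-CT bullet in 3.6.4, section 3.5 and Table 1 to one fixed imaging interval instead of a range. The choice of interval belongs to the investigators; 12 weeks is the only fixed one the documents state. Give the same scan weeks in both arms, counted from a date both arms have (LPFS already runs from randomization), with a stated window around each scan. Continue the calendar for as long as the regional and distant PFS endpoints in section 5.1 need it, so it should not end at local progression. Clinic and quality-of-life visits may keep the three-to-six-month range if they are separated from imaging in the text and the table.

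The cost is protocol wording and one table. If 12 weeks is kept, essentially no scan is added beyond what the bullet already asks for. The small downside is less flexibility in scheduling scans. The sample size is unaffected.

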3.6.5 Methods of Measurement

The methods of measurement are as follows:

CT, PET/CT, or MRI are the best currently available methods for measuring disease status. Lesions that can be accurately measured in at least one dimension $\geq 10\text{mm}$ (1.0 cm). If measurable disease is restricted to a solitary lesion, its neoplastic nature should be confirmed by cytology/histology.

Clinically detected lesion will only be considered measurable when superficial (vis-à-vis skin nodules and palpable lymph nodes). Documentation should include color photography and ruler estimation of size.

3.6.6 Evaluation of Disease Status and Survival

Survival and time to progression will be measured from the date of salvage surgery to date of death, appearance of new metastatic lesion, or objective tumor progression.

4.0 SUBJECT SELECTION AND ELIGIBILITY

4.1 Selection of subjects

Forty-two (42) patients with recurrent or second-primary head-and-neck squamous cell carcinomas within a previously-irradiated field with high-risk features (compromised/positive surgical margins or extra-nodal extension) following macroscopic complete (R0/R1) salvage surgery will be recruited for this randomized phase II study.

4.2 Identification and initiation of contact with study participants

Potential research subjects are first identified by their primary doctor/clinical team. The research project will be discussed by the caregiver with the patient. If interested, the patient will be informed at this time either to contact the research team to express his/her interest in participating. Other subjects are referred in specifically for possible participation in a study which they or their physicians are aware of based on publications which list clinical trials at UPCI. "Cold-calling" will not be used to recruit subjects. Potential subjects will be approached by clinicians who are directly involved in their care. "Finder's fees" for referring a potential subject for participation in a research study are prohibited.

Physicians and other health care professionals in the area are aware of active studies at UPMC Radiation Oncology Department by means of various publications including the World Wide Web. Such publication and Web listings are not advertisements for specific studies. Rather, they are public listings of trials available.

Once a subject is identified as a potential participant in a research study as indicated above, he/she is screened for eligibility. No identifiable information (e.g. name, diagnosis, treatment, etc.) will be released until the subject has given written authorization. No research-related procedures (including review of the subject's medical records) will be performed until the subject has provided written informed consent. The consent process will be carried out as a joint effort among the subject's physicians, the study coordinators, and a physician who is listed as an investigator on the study.

4.3 Inclusion criteria

Each patient must meet all of the following inclusion criteria for study enrollment:

- Age ≥ 18 with ability to provide written informed consent
- Pathologically proven recurrent or second-primary head-and-neck cancer receiving prior radiotherapy with or without chemotherapy
- Prior radiotherapy to a dose of $\geq 50\text{Gy}$
- No evidence of distant metastases
- Macroscopic complete salvage surgery with curative intent (surgery was not performed only for biopsy or palliation). Final pathology and imaging must indicate a R0 or R1 resection (no gross disease remaining).
- High-risk pathologic features must be present: compromised/positive surgical margins ($\leq 2\text{mm}$) or extra-nodal extension (patient with other high-risk features gross perineural invasion, bone invasion, angiolytic invasion, or a constellation of these factors may be eligible based on case-by-case basis at discretion of principal investigator).
- Karnofsky Performance Status ≥ 60 (ECOG 0-2)

- Any number or type of prior chemotherapy is allowed (patient may receive concurrent or adjuvant systemic therapy such as cetuximab at the discretion of the treating oncologic team).

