1.0 BACKGROUND

1.1 Salvage Surgery for Recurrent Head-and-Neck Cancers

Recurrent and second-primary head-and-neck cancers (rHNC) in a previously-irradiated field represent a therapeutic challenge (1). Even with adjuvant therapy, rHNC occurs in $\geq 20\text{-}30\%$ of high-risk postoperative patients and $\geq 30\%$ of patients treated with definitive chemoradiotherapy (2-3). While there are no randomized data to test the benefits of salvage surgery after prior irradiation, for patients who can have surgical resection, based on available data, surgical resection represents the currently accepted standard of care (4-5). However, even patients with resectable rHNC are at high-risk for subsequent failure (67% overall failure rates). In patients with close or positive surgical margins following salvage surgery, recurrence rates of nearly 100% have been reported (6). To improve tumor control in this setting adjuvant re-irradiation techniques along with chemotherapy has been used with mixed but limited success (7-10).

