3.0 INVESTIGATIONAL PLAN

3.1 Overall design and plan of the study

Detailed visit-by-visit study procedures and a study flow chart are provided in Section 6.3. Prior to enrollment, all subjects will be evaluated with medical records to confirm patient received diagnosis of recurrent or second-primary head-and-neck squamous cell carcinomas. Additionally, these records will confirm the patient had had macroscopic complete (R0/R1) salvage surgery and previous radiation. Patients will receive a Stereotactic Body Radiotherapy and then followed periodically for up until 2 years.

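### Does the inclusion list in section 4.3 let in patients outside the population that section 4.1 describes, and does that matter?

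*Combined protocol and SAP*

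**What the plan says.** The population is described in several places of the combined protocol and SAP.

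- **4.1 Selection of subjects** recruits 42 patients with "recurrent or second-primary head-and-neck squamous cell carcinomas within a previously-irradiated field with high-risk features (compromised/positive surgical margins or extra-nodal extension", after macroscopically complete salvage surgery.
- **4.3 Inclusion criteria**, every item of which each patient has to meet, asks for "Pathologically proven recurrent or second-primary head-and-neck cancer receiving prior radiotherapy with or without chemotherapy". A separate item sets the prior dose at 50 Gy or more. Neither says where that dose was given relative to the new disease.
- **4.3**, in the item on risk features, repeats the two features of 4.1 and then adds that a "patient with other high-risk features gross perineural invasion, bone invasion, angiolytic invasion, or a constellation of these factors may be eligible", case by case, at the principal investigator's discretion.
- **3.1 Overall design** has the records reviewed before enrolment to "confirm patient received diagnosis of recurrent or second-primary head-and-neck squamous cell carcinomas", and says that "these records will confirm the patient had had macroscopic complete (R0/R1) salvage surgery and previous radiation".
- **3.2, 3.6.1 and 4.4** say nothing about the old field.
- **1.1** opens with the same in-field framing as 4.1: "Recurrent and second-primary head-and-neck cancers (rHNC) in a previously-irradiated field represent a therapeutic challenge".

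**The concern.** A coordinator who works only from the 4.3 list has no in-field item to tick. A squamous second primary outside the old field, in a patient who once had at least 50 Gy, would pass 3.1 and could meet every item in 4.3, yet would not belong to the population in 4.1. Second primaries are expressly admitted, so such a patient is conceivable. In the same way, a patient whose only risk feature is perineural, bone or angiolytic invasion can enter under 4.3, although 4.1 names only margins and extra-nodal extension.

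What would be at stake is whom the results describe. All randomised patients enter the LPFS comparison (6.3). A treated out-of-field patient would also enter the SBRT toxicity percentages (6.4), although objective 2.3 concerns toxicity of re-irradiation. Section 1.1 cites 67% failure overall in resectable disease and nearly 100% after close or positive margins, so the protocol itself treats margin status as prognostic. A different case mix could in principle move the control-arm rate away from the 20% assumed in 6.2.

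**Working it through.** **1. The sections side by side.**

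| Feature | 4.1 | 4.3 | Record review in 3.1 |
|---|---|---|---|
| Disease inside the old field | required | not repeated | previous radiation only |
| Margins or extra-nodal extension | required | required, with a discretionary exception | not mentioned |
| Squamous histology | required | not repeated | confirmed |
| Prior dose of at least 50 Gy | not mentioned | required | not mentioned |

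Neither section is complete alone: 4.1 lacks the dose floor and 4.3 lacks the field. Both belong to chapter 4.0, on selection and eligibility. The items in 4.3 are necessary conditions, and nothing says they replace 4.1. Read together, they require in-field disease and at least 50 Gy. For risk features, 4.1 does not say that its two are exhaustive, and 4.3 states its exception openly.

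**2. The plan's own figure (6.2).** Inputs: one-year LPFS 20% and 52%, one-sided alpha 0.10, power 90%, two years of accrual plus one of follow-up, 5% loss in each arm.

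- Under exponential survival, HR = ln(0.52)/ln(0.20) = 0.654/1.609 = 0.406.
- Schoenfeld events = 4(1.2816 + 1.2816)² / (ln 0.406)² = 26.28/0.811 = 32.4, rounded up to 33.
- Event probability with uniform accrual = 1 − [exp(−h) − exp(−3h)]/(2h). This is 0.940 for control (h = 1.609) and 0.710 for SBRT (h = 0.654), mean 0.825.
- Patients = 33/0.825 = 40.0, and 40.0/0.95 = 42.1, against the stated 42.
- With 42 patients and 5% loss, expected events are 42 × 0.95 × 0.825 = 32.9, and power is 90.4%.

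The stated size reproduces. Freedman's formula would give 37 events and about 47 to 48 patients, but that is a choice of method and has no bearing on eligibility.

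**3. Weight of one patient.** 1/42 = 2.4% of the efficacy set. If all 21 assigned to SBRT are treated, 1/21 = 4.8% of the toxicity denominator.

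**4. Bias.** Under 3.6.2 a patient is randomised only after being judged eligible, and 6.3 analyses patients as assigned. A wider entry gate therefore acts on both arms alike. In simulations with no treatment effect in anyone, the one-sided type I error was 0.105 without out-of-population patients and 0.102 to 0.106 with 10% to 20% of them.

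**5. Power, by assumption only.** The documents give no share, prognosis or treatment effect for such patients. Simulated trials used the 6.2 inputs, with loss taken as 5% per year, and had a base power of 90.1%. Control one-year LPFS in the extra patients was varied from 5% to 70%. With 2 of 42 such patients, power was 87.2% to 90.2% if the planned HR also held in them, and 86.0% to 88.3% if SBRT did nothing in them. At a 20% share the ranges were 79.3% to 90.2% and 70.4% to 79.4%. Nothing in the documents supports a 20% share or a zero effect.

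**The case for a change.** The best case for acting is that 4.1 describes who will be recruited, while 4.3 is what each patient must satisfy; in practice the list is what gets applied. The title's reference to previous irradiation describes the patient and does not locate the tumour. The screening lists in 3.2 and 3.6.1 also skip prior dose and Karnofsky status, but those are at least criteria in 4.3, whereas field location is in neither place. In a trial of 42, each patient counts, and the repair would be a few words.

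The textual part stands: 4.3 is wider in wording, and no listed enrolment step names the field. The inference from it is weaker. The intent is stated in 4.1 and again in 1.1, and the review in 3.1 already covers previous radiation, so the reviewer is in the records where its location would be sought. On risk features, the contrast in 1.1 concerns margins, carries no time point, and says nothing about perineural, bone or angiolytic invasion, so no harm from the discretionary route is shown. The larger power losses in the illustration come from assumed shares and effects, and are not evidence that the trial is short of patients.

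**Conclusion.** The concern is right about the wording but does not call for a change. A team that applies 4.1 and 4.3 together enrols the intended population and obtains a valid comparison. Copying the field phrase into 4.3 would restate a rule the protocol already contains. Aligning the risk-feature statements would only record a choice that 4.3 already makes openly. Histology is settled by 3.1.

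The consequence is confined to description: 2.4% of the efficacy set per out-of-field patient, and 4.8% of the toxicity denominator if that patient is treated, for a number of patients that may be zero. Analysts can handle this without altering the plan, by tabulating the qualifying risk feature and, where records allow, the relation to the old field among the baseline characteristics, which 6.4 already allows in exploratory Cox models.

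This rests on three assumptions: that staff read 4.1 as part of eligibility, that eligibility is decided without knowledge of the coming allocation, and that few or no out-of-field patients are enrolled. The documents support the first by where 4.1 is placed and the second by the sequence in 3.6.2. They are silent on the third.
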